8.3.1.6. Steroid Impact Questionnaire

The benefits, side effects and impact of steroids on GCA symptoms and subjects will be assessed using a GCA disease-specific subject-reported questionnaire, the Steroid Impact Questionnaire (SIQ). The SIQ contains 32 and 21 items at baseline and post-baseline visits, respectively. The SIQ assesses items in the following categories:

- Steroid Dose/Duration
- General Impact
- Benefits
- Work/Productivity
- Side Effects
- Emotions
- Overall Satisfaction

All the SIQ data will be listed.

8.3.1.7. 36-Item Short Form Version 2 Acute (SF-36v2 Acute)

The SF-36v2 acute health survey questionnaire was developed as part of the Rand Health Insurance Experiment and consists of the following 8 multi-item scales:

- Limitations in physical functioning due to health problems
- Limitations in usual role activities due to physical health problems
- Bodily pain
- General mental health (psychological distress and well-being)
- Limitations in usual role activities due to personal or emotional problems
- Limitations in social functioning due to physical or mental health problems
- Vitality (energy and fatigue)
- General health perception

These 8 scales are scored from 0 to 100 with higher scores indicating better health. Another algorithm yields 2 summary scores, the Physical Component Summary (PCS) score and Mental Component Summary (MCS) score. These summary scores are also scaled with higher scores indicating better health.

Normalized scores based on the 2009 United States general population will be generated by QM Certified Scoring (Software) version 4.5 (QualityMetric, Inc, Lincoln, RI, USA). This software will be used to generate the scores used in the outputs. The full description of the derivations and the missing questions handling rules are described in the manual. All the default approaches will be used to derive these values. In particular, summary scores (PCS and MCS) will be set to missing if the subject is missing any one of the 8 individual domains.

The following endpoints will be summarized by treatment group and visit:

- Absolute and change from baseline in the 2 summary scores (a positive change from baseline reflects an improvement).

All SF-36v2 acute data will be listed.

8.3.1.8. EuroQoL-5Dimensions, 5 Levels

EQ-5D essentially consists of 2 elements: the EQ-5D descriptive system and the EQ visual analogue scale (EQ VAS).

The EQ-5D descriptive system comprises the following 5 dimensions:

- Mobility
- Self-Care
- Usual Activities
- Pain/Discomfort
- Anxiety/Depression

Each of these 5 dimensions has 5 levels: 1: no problems; 2: slight problems; 3: moderate problems; 4: severe problems; 5: Unable to do.

The digits for each of the 5 dimensions can be combined in a 5-digit number describing the subject's health state: e.g. state 11111 indicates no problem on any of the 5 dimensions, while state 12345 indicates no problems with Mobility, slight problems with Self-Care, moderate problems with doing Usual Activities, severe Pain or Discomfort and extreme Anxiety or Depression. A total of 3125 possible health states is defined, therefore the health states will not be summarized. Instead, the health states will be converted into a single summary index (EQ-5D Index) by applying a formula that attaches weights to each of the levels in each dimension. The weights based from the UK population will be used for the conversion, regardless of the origin country of the subject.

In order to create the EQ-5D Index (Utility Index), the conversion provided from the "EQ-5D-5L Crosswalk Index Value Calculator" Excel file will be used. This file is downloadable from: http://www.euroqol.org/fileadmin/user_upload/Documenten/Excel/Crosswalk_5L/EQ-5D-5L_Crosswalk_Index_Value_Calculator.v2.xls. [Van Hout B, Janssen MF, et al.]. The "UK" column of the "EQ-5D-5L Value Sets" sheet will be used for the conversion.

The EQ VAS records the subject's self-rated health on a 20-cm vertical VAS where the endpoints are labelled 'best imaginable health state' (score of 100) and 'worst imaginable health state' (score of 0). The EQ VAS can be used as a quantitative measure of health outcome as judged by the individual subjects.

The following endpoints will be summarized by treatment group and visit:

- Absolute and change from baseline in EQ-5D index (Utility Index)
- Absolute and change from baseline in EQ-5D VAS

For both changes from baseline, a negative change indicates an improvement, and a positive change indicates a worsening.

All EQ-5D-5L data (raw and derived) will be listed. Conversion between each of the 5-digit numbers and associated weight will be listed.

9. Safety Analyses

All safety analyses will be performed on the Safety set. Subjects will be analyzed according to the treatment actually received, regardless of the treatment group they were randomized to. Percentages for safety summaries based on the number of subjects with a given event or attribute will be based on Safety set. All safety data will be included in listings.

9.1. Adverse Events

The definition of an AE is detailed in Section 12.4.1 in Appendix 4 of the protocol.

Treatment-emergent AEs:

A treatment-emergent AE for Part A is defined as an AE with a start date during the exposed period.

The exposed period is defined as the period from the 1st dose of SC IP to:

- Early withdrawal: last dose of SC IP + 16 weeks

- Completers (subjects who attended the week 52 visit):
 - Week 52 visit if entering into part B
 - Last dose of SC IP + 16 weeks if not entering into part B

Unless otherwise specified, AE outputs will be based on TEAEs.

All AEs will be coded by system organ class (SOC) and preferred term (PT) according to the Medical Dictionary for Regulatory Activities (MedDRA, Version 19.0 or higher).

An overview summary of TEAEs, including counts and percentages of subjects will be generated by actual treatment group, with any of the following categories:

- Any TEAE, TEAEs related to study treatment (SC IP and/or prednisone study drug), TEAEs leading to permanent discontinuation of study treatment, TEAEs leading to dose interruption/delay, TEAEs leading to dose reduction, TEAEs leading to dose increase, TEAEs leading to dose not changed.
- Any serious TEAEs, serious TEAEs related to study treatment (SC IP and/or prednisone study drug), fatal serious TEAEs, and fatal serious TEAEs related to study treatment.
- Any TEAE of special interest (TEAESI) (see [section 9.1.8](#) for further details), TEAESIs related to study treatments (SC IP and/or prednisone study drug), TEAESIs leading to permanent discontinuation of study treatment, TEAESIs leading to dose reduction, TEAESIs leading to dose increase, TEAESIs leading to dose not changed, TEAESIs leading to dose interruption/delay.

A listing presenting the relationship between SOC, PT, and AE reported will be provided.

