1.1. Changes in the Planned Analysis due to Study Termination

This SAP reflects the analyses done given study termination, and are not aligned with planned analyses as per protocol.

Due to the sponsor's decision to terminate the study, data for the following endpoints/objectives are not available. Therefore, the following objectives will not be reported in this planned analysis:

- Pharmacokinetic objectives
- Immunogenicity objectives
- Pharmacodynamic objectives
- Pharmacogenetics objectives
- Vascular ultrasound objectives

Additionally:

- Available data for exploratory objectives / endpoints related to biomarkers will only be listed.
- No statistical analysis will be carried out for efficacy objectives / endpoints due to the limited number of subjects completing the study at week 52.
- However, [Section 2.1](#) and [Section 3.2](#) list respectively objectives and endpoints as specified in the protocol.
- Protocol endpoint "Median and cumulative prednisone dose over time" is modified to "Cumulative prednisone dose over time" as median prednisone dose will be provided as part of the summary statistics for cumulative prednisone dose.
- Protocol wording "GCA flare" is modified to "disease flare" for consistency across endpoints in this document.

Due to study termination on 10th October 2017, early withdrawal visits were completed for all subjects by 30th November 2017. All subjects are required to have a safety follow-up visit 16 weeks (+/- 1 week) after the early withdrawal visit. The study should be terminated for an individual subject after they have completed the 16-week safety follow-up visit, unless there is a need for additional post-study visits for continued evaluation of an ongoing adverse event. However, if an anti-IL6, any biologic or investigational agent is initiated, the subject will be withdrawn from the 16-week safety follow up.

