5.1. Disposition

The number of subjects in each of the sets will be summarized. All subjects screened will be presented overall and the Randomized set, ITT set, and Safety set will be summarized overall and by treatment group using the all subjects screened set.

A summary of the subjects excluded from each analysis set and the reasons for exclusion will be presented using the Randomized set. This summary will include the number and percentage of subjects for the following categories: subjects excluded from the ITT set and reasons, and subjects excluded from the Safety set and reasons. Percentages for exclusion reasons will be based on the number of subjects excluded from the specific analysis set being summarized. Subjects could be excluded from an analysis set for more than one reason. A listing of subjects included in any analysis set as well as a listing of subjects excluded from any analysis set will be produced.

The number of subjects by country will be summarized by treatment group and overall.

A summary of subject status and reason for study withdrawal will be provided. The status section will display:

For Part A:

- Subjects who attended the Week 52 Visit with the following subcategories:
 - Did not enter Part B, defined as subjects who completed week 52 visit and did not enter Part B
 - Completed Safety Follow-up
 - Not Completed Safety Follow-up
 - Enter Part B, defined as subjects who were enrolled in Part B
- Early withdrawal or study termination:
 - Early withdrawal, is defined as subjects who permanently discontinued SC IP and prednisone study drug treatments prior to completing week 52 visit AND withdrew from the study.
 - Study termination is defined as subjects who were still in the study as of study termination date of 10 Oct 2017.

This includes the following subcategory:

- Completed Safety Follow-up, defined as the 16 week safety follow up after withdrawal or study termination
- Not Completed Safety Follow-up

For Part B:

- Completed Week 104 visit, defined as subjects who completed Part B
 - Completed Safety Follow-up
 - Not Completed Safety Follow-up
- Early withdrawal or Study Termination with the following subcategory:

- Completed Safety Follow-up, defined as subjects who attended the safety follow up period after withdrawal or study termination
- Not Completed Safety Follow-up

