7.2. Study Treatments

7.2.1. Extent of Exposure

Listings of exposure to SC IP and prednisone study drug will be provided.

A summary of SC IP exposure will be provided. The following 3 parameters will be reported on the Safety set:

- Total number of injections a subject receives.
- Duration of SC IP treatment (weeks): defined as (Date of last SC IP dose – Date of first SC IP dose + 1 day) / 7. Only complete dates will be used when calculating duration of treatment. First and last injection dates will be used, regardless of any missed doses.
- Duration of SC IP exposure (weeks): defined as (Date of last SC IP dose – Date of first SC IP dose + 112 days) / 7, where 112 days corresponds to 16 weeks. Only complete dates will be used when calculating duration of exposure. First and last injection dates will be used, regardless of any missed doses.
- Cumulative SC IP dose: defined as the total dose in mg (SC IP or placebo) a subject receives.

A summary of prednisone study drug exposure will be provided. The following 2 parameters will be reported on the Safety set:

- Duration of prednisone study drug treatment (weeks): defined as (Date of last non-zero dose from the taper [i.e. the last prednisone end date from taper with a non-zero dose recorded] – Date of first dose from the taper + 1 day) / 7.
- Cumulative prednisone study drug dose (mg): defined as the total dose in mg a subject receives. For each week of the taper (both open-label and blinded), cumulative dose will be calculated as: the number of days x expected doses, the expected dose depending on the pre-specified taper schedule. Overall cumulative dose will be the sum of the cumulative doses of each week.

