9.1.1. Incidence of Adverse Events

Summaries of the total number of TEAEs and the number and percentage of subjects with at least 1 TEAE will be provided by actual treatment group and ordered by SOC and PT. This summary will be repeated for pre-study treatment (i.e. AEs starting before the exposed period as defined in [Section 9.1](#)) and post-study treatment AEs (i.e. AEs starting after the exposed period as defined in [Section 9.1](#)).

Treatment-emergent AEs will be presented in descending order from the SOC with the highest total incidence (that is, summed across all treatment groups) to the SOC with the lowest total incidence. If the total incidence for any 2 or more SOCs is equal, the SOCs will be presented in alphabetical order. Within each SOC, the PTs will be presented in alphabetical order. At each level of subject summarization, a subject is counted once if the subject reported 1 or more events.

Common AEs are defined as those reported by more than 5% of the subjects in any of the treatment arm. Summaries of common AEs and common non-serious AEs will be provided (no rounding for the percentage will be used in terms of 5% threshold, e.g. event with 4.9% incidence rate should not be included in this table). The summary will be displayed in descending order of incidence in total column by PT only.

The proportions of subjects with common AEs and relative risks will be summarized for the six comparisons. This will be done using the RELRISK option of the table statement of the SAS PROC FREQ procedure.

Incidences per 100 subject-year will be calculated for the 3 groups of AEs described below, for each SOC and PT. The table will include the number of subjects and AEs, the total subject-years of exposure, the incidence per 100 subject-years of exposure as well as the 95%CI (exact Poisson confidence intervals). For each subject, the duration of exposure is defined as follows:

- For subjects who have an event: from 1st dose of SC IP until the occurrence of the first event.
- For subjects who do not have an event: duration of exposed period.

The exposure-adjusted incidence rates will be calculated for 3 groups of AEs:

- All AESIs (for each category, SOC and PT)
- All fatal serious AEs (for each SOC and PT)
- All SAEs (for each SOC and PT)

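### SAP 9.1.1 counts person-time to last dose + 16 weeks even when safety follow-up has ended, so the exposure-adjusted AESI, SAE and fatal-SAE rates are understated

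*SAP*

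**What the plan says.** SAP 9.1 defines the exposed period, which runs from the first SC IP dose. For subjects who leave early its end is "Early withdrawal: last dose of SC IP + 16 weeks". For those who attend Week 52 but do not continue, it is "Last dose of SC IP + 16 weeks if not entering into part B". Part B entrants stop at the Week 52 visit and are not at issue.

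SAP 9.1.1 builds the denominators of the exposure-adjusted rates from that period. These rates are planned for AESIs, SAEs and fatal SAEs, by SOC and PT, with exact Poisson intervals. The two person-time rules are "For subjects who have an event: from 1st dose of SC IP until the occurrence of the first event" and "For subjects who do not have an event: duration of exposed period".

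SAP 1.1 sets the follow-up that applies after termination: a safety visit 16 weeks after the early withdrawal visit, with one exception: "if an anti-IL6, any biologic or investigational agent is initiated, the subject will be withdrawn from the 16-week safety follow up". The disposition table in SAP 5.1 has a category for "Not Completed Safety Follow-up".

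Protocol 7.5.1.1 collects adverse events up to the follow-up contact. After that, investigators need not look for events in former subjects, although they must notify the sponsor of a related SAE that they learn of.

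**The concern.** One rule ends observation early; another keeps the exposure clock running to a fixed date. An event-free subject who leaves follow-up before last dose + 16 weeks adds time to the denominator during which nobody was actively collecting events. The error goes one way: the stated rate is lower than the rate over observed time.

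Starting another agent is only one route. Loss to follow-up and withdrawal of consent leave the same gap. So does death, and that case needs no assumption about switching. Rates are calculated for each SOC and PT, so a subject who dies of one event is event-free in the other rows and still contributes time after death up to the nominal end date. SAP 4.6.4 already caps imputed end dates at death; the person-time rule has no equivalent.

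These rates matter more than usual here. SAP 1.1 drops statistical analysis of efficacy, so safety is a main remaining output. Termination also shortened treatment for many subjects, which makes the 16-week tail a larger share of their person-time.

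**Working it through.** **The plan's own figure.** SAP 7.2.1 expresses the post-dose window in days ("where 112 days corresponds to 16 weeks"): 16 × 7 = 112, which reproduces. The documents state no adverse-event rate, so no rate can be reproduced.

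**Inputs.** The 16-week tail is from SAP 9.1. The documents give none of the following, so they are assumed:
- T, weeks from first to last SC IP dose
- f, the share of subjects who leave follow-up early
- u, weeks from last dose to leaving (u < 16)

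**Formulas.** Counted person-time per subject is T + 16. Observed person-time is (T + 16) − f(16 − u). For rare events:

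stated rate / rate on observed time = 1 − f(16 − u)/(T + 16)

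**One subject,** T = 26, u = 4: counted 26 + 16 = 42 weeks, observed 26 + 4 = 30 weeks, 42/30 = 1.40.

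**One arm,** T = 26, u = 4; overstatement = 42/(42 − 12f):

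| f | Person-time counted / observed | Stated rate / rate on observed time |
|---|---|---|
| 0 | 1.000 | 1.000 |
| 0.10 | 42/40.8 = 1.029 | 0.971 |
| 0.20 | 42/39.6 = 1.061 | 0.943 |
| 0.30 | 42/38.4 = 1.094 | 0.914 |

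**Range over other assumed values:**
- T = 50, f = 0.10, u = 8: 1 − 0.8/66 = 0.988
- T = 26, f = 0.25, u = 4: 1 − 3/42 = 0.929
- T = 12, f = 0.50, u = 2: 1 − 7/28 = 0.750

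The understatement therefore runs from about 1% to 25%. A constant-hazard check with time-to-first-event denominators and a true rate of 15 per 100 subject-years gives 14.83, 13.96 and 11.27 for these three cases, which agrees with the rare-event formula.

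**Illustrative arm.** Take 34 subjects, T = 26, 8 leaving at u = 4, and 3 events, with event subjects given full time for simplicity. Counted: 34 × 42 = 1,428 weeks = 27.37 subject-years. Observed: 26 × 42 + 8 × 30 = 1,332 weeks = 25.53 subject-years. The rates are 3/27.37 = 10.96 and 3/25.53 = 11.75 per 100 subject-years, so the stated rate is about 7% too low.

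**Interval.** The exact Poisson limits for 3 events are about 0.62 and 8.77 events. Dividing by the two denominators gives about 2.3 to 32 and about 2.4 to 34 per 100 subject-years. Estimate and limits all shift by the same factor, so the ratio of upper to lower limit does not change.

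**The case against.** The strongest reply is that this affects descriptive rates in a terminated study, by an amount nobody can state. Much of that stands. The number and timing of early exits are not in the documents. At 10% to 20% exiting, the error of roughly 3% to 6% is small beside a 14-fold Poisson interval on 3 events. Follow-up is also timed from the early withdrawal visit, not from the last dose, so any gap between the two is observed, and a subject who switches late may add no unobserved time. Subjects who stop SC IP but stay in the study remain observed.

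Four stronger readings are tempting, and the documents do not support them.

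- **That the sirukumab-versus-placebo safety comparison is biased.** The SAP plans no ratio of exposure-adjusted rates. Its between-arm measures are relative risks of subject proportions (SAP 9.1.1 and 9.1.8), and safety percentages use Safety-set counts (SAP 9). These can miss events after exit but have no person-time denominator. Someone setting arm rates side by side could be misled if early exit differed by arm, but nothing in the documents shows that it does.
- **That the intervals gain false precision.** Relative precision is unchanged; the whole interval is too low.
- **That no event could be recorded after exit.** Protocol 7.5.1.1 still requires notification of a related SAE that comes to the investigator's attention. Active collection stops; recording does not stop altogether. A fatal SAE likewise ends that subject's time in the rows it belongs to.
- **That SAP 7.2.1 has the same fault.** Its duration of exposure describes dosing plus a fixed window and is not a rate denominator.

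Nor is the disposition category in SAP 5.1 a forecast of how many will leave. It shows only that the case is provided for.

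**Conclusion.** The point stands within these limits. SAP 9.1, 9.1.1 and 1.1 together count time without active collection, and time after death in other SOC and PT rows, as event-free exposure. No cap appears elsewhere in the SAP. The direction is certain wherever an event-free subject leaves before the nominal end: the AESI, SAE and fatal-SAE rates and both their limits are too low.

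The size is conditional. The central illustration, a 3% to 9% overstatement of person-time, rests wholly on assumed values for time on drug, time of exit and share exiting. It falls to zero if every subject is followed for the full window. This is worth correcting because the plan's own rule produces the error and the correction is cheap. It does not call the other safety tables into question.

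**What to change.** Leave the exposed period in SAP 9.1 unchanged. It also defines treatment-emergent events, so shortening it could move an SAE or death reported after exit, but within 16 weeks of the last dose, out of the main tables and into the post-treatment summary. SAP 7.2.1 can also stay as it is.

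In SAP 9.1.1, define person-time for a subject without an event as first SC IP dose to the earliest of:
- the end of the exposed period;
- death;
- last safety contact or withdrawal from follow-up, including withdrawal on starting another anti-IL6, biologic or investigational agent.

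Also state how the rate numerator treats an event reported after that date but inside the treatment-emergent window, so that numerator and denominator match. One consistent choice is to keep such an event in the treatment-emergent tables and listings, leave it out of the rate numerator, and end that subject's person-time at the cap.

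The cost is a sentence or two in the SAP, a minimum-of-dates derivation, and slightly higher stated rates. If nobody's follow-up was cut short, no rate changes.

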#### **5.4.2. Discontinuation of Study Drug**

Permanent discontinuation of study drug will not require the subject to be withdrawn from the study. Subjects should continue where possible to be followed and disease status assessed. Upon permanent discontinuation of subcutaneously-administered blinded sirukumab or matching placebo, corticosteroid dose and treatment will be at the discretion of the investigator.

Study drug (subcutaneously-administered blinded sirukumab or matching placebo) must be permanently discontinued for any of the following:

1. The investigator (in consultation with the medical monitor) believes that for safety reasons (e.g., adverse event) it is in the best interest of the subject to stop treatment.
2. Severe allergic reaction or anaphylactic reaction resulting in bronchospasm with wheezing, or dyspnea requiring ventilatory support, or symptomatic hypotension with a > 40 mmHg decrease in systolic blood pressure that occurs following study drug administration.
3. Reaction suggestive of serum sickness occurring 1-14 days after study drug administration. These may be manifested by symptoms of myalgias, arthralgias, fever, rash, pruritus, facial, hand, or lip edema, dysphagia, urticaria, sore throat, and/or headache.

4. Adverse events (AEs) or laboratory abnormalities indicative of safety concerns which are significant enough to discontinue study drug in the opinion of the investigator.
5. Pregnancy.
6. Liver function abnormalities as specified in Section 5.4.3.
7. Opportunistic infection, ie, an infection by an organism that usually causes disease only in a host whose resistance is lowered (eg, Pneumocystis jirovecii, coccidioidomycosis, Mycobacterium avium).
8. Active or latent TB.
9. Malignancy, excluding nonmelanoma skin cancer.
10. Demyelination, either central or peripheral.
11. Two confirmed consecutive absolute neutrophil counts of  $<0.5 \times 10^9$  cells/L.
12. Two confirmed consecutive platelet counts  $<50 \times 10^9$  cells/L.
13. Acute diverticulitis requiring antibiotic treatment.
14. Gastrointestinal perforation.

Subjects must **not** receive blinded subcutaneous sirukumab or matching placebo during the course of a serious infection. Subjects who temporarily discontinue blinded sirukumab or matching placebo due to an infection or other reasons should continue to follow the prednisone taper schedule.

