4.6. Handling of Missing Data

4.6.1. Treatment Failure Definition

For the primary endpoint derivation, a treatment failure is defined as any subject who:

1. Discontinued permanently SC IP prior to completing week 52 visit due to any reason and continued in the study (i.e. follow-up off treatment)
- or
2. Withdrew from the study for any reason earlier than 10th October 2017, the study termination date.

A subject will be considered a treatment failure from the earliest date that the subject meets any of the 2 treatment failure criteria. Only withdrawals prior to 10th October 2017 will be considered, withdrawals on or after this date will likely be result of study termination at sponsor's request and not provide an accurate summary of treatment response.

A subject that temporarily has their treatment of SC IP put on hold, will not be considered as permanent discontinuations.

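### SAP 9.1 lets the Part A exposed period run past last dose + 16 weeks for Part B entrants whose last SC IP dose was before about Week 36

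*SAP*

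**What the plan says.** SAP 9.1 ties treatment emergence to one window: "A treatment-emergent AE for Part A is defined as an AE with a start date during the exposed period". The window opens at the first SC IP dose, and its end depends on the class of subject:

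- "Early withdrawal: last dose of SC IP + 16 weeks".
- Completers who do not go on: "Last dose of SC IP + 16 weeks if not entering into part B".
- Completers who do go on: "Week 52 visit if entering into part B".

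Completers are identified by attendance alone: "Completers (subjects who attended the week 52 visit". Being on SC IP at that visit is not required.

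SAP 9.1.1 uses the same window as the denominator of the rates per 100 subject-years for AESIs, SAEs and fatal SAEs: "For subjects who do not have an event: duration of exposed period". AEs that start after the window go to a separate post-study-treatment summary.

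The plan foresees subjects who stop SC IP and stay. Protocol 5.4.2 states: "Permanent discontinuation of study drug will not require the subject to be withdrawn from the study". SAP 4.6.1 describes subjects who stopped SC IP before Week 52 and "continued in the study (i.e. follow-up off treatment". SAP 5.1 reserves early withdrawal for subjects who also left the study. The Part B analysis sets (SAP 11.1.1 and 11.1.2) require only one Part A dose of SC IP and entry into Part B.

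**The concern.** Two subjects with the same dosing history can be handled differently because one later enters Part B and the other does not. Suppose both stop SC IP at Week 12 and both attend Week 52. An AE at Week 40 is treatment-emergent for the one who enters Part B and post-study-treatment for the other. The entrant, if event-free, contributes nearly twice the person-time.

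The rule also sits badly with the SAP's other uses of exposure. SAP 7.2.1 reports SC IP exposure as last dose minus first dose plus 112 days. SAP 11.5 calls a Part B event exposed only if it falls within 16 weeks after sirukumab.

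AE outputs are based on TEAEs by default, and the same window drives the exposure-adjusted rates. With efficacy reduced to summary statistics after termination, safety tables carry most of the report, so the window should follow drug exposure and not a later choice about Part B.

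**Working it through.** **The plan's own figure.** SAP 7.2.1 equates 16 weeks with 112 days: 16 × 7 = 112. This reproduces.

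**Inputs.** First dose at Week 0; last Part A SC IP dose at week L; Part A visit at Week 52; post-dose window of 16 weeks (SAP 7.2.1, 9.1, 11.5).

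**Formulas.**
- SAP 9.1, Part B entrant: window = 52 weeks.
- SAP 9.1, other classes: window = L + 16 weeks.
- Consistent rule for entrants: min(52, L + 16).
- Excess = 52 − min(52, L + 16) = max(0, 36 − L) weeks.

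| L (week) | SAP 9.1, entrant | min(52, L + 16) | Excess (weeks) |
|---|---|---|---|
| 4 | 52 | 20 | 32 |
| 8 | 52 | 24 | 28 |
| 12 | 52 | 28 | 24 |
| 24 | 52 | 40 | 12 |
| 34 | 52 | 50 | 2 |
| 36 or later | 52 | 52 | 0 |

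The discrepancy disappears at L = 36.

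**One subject across the SAP.** Take a sirukumab subject with L = 12 who enters Part B and takes no open-label drug. The exposure table (7.2.1) gives 28 weeks. The rate denominator (9.1.1) gives 52 weeks if event-free. An AE at Week 51 is treatment-emergent under 9.1, while an AE shortly after Week 52 is non-exposed under 11.5, although both fall well beyond Week 28.

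**Arm level.** Assume every other subject is counted for 52 weeks, there are no events, and a share f of the arm has last dose at week L and enters Part B. The overstatement is 52 / (52 − f × (36 − L)) − 1. Arm size cancels.

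| Assumed share f | L = 4 | L = 12 | L = 24 |
|---|---|---|---|
| 5% | 3.2% | 2.4% | 1.2% |
| 10% | 6.6% | 4.8% | 2.4% |
| 20% | 14.0% | 10.2% | 4.8% |

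Example: f = 10%, L = 12 gives 52 / (52 − 2.4) − 1 = 52 / 49.6 − 1 = 4.8%. The documents give no value for f.

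**Direction.** Let r1 be the event rate inside the 16-week window over time T1, and r2 the rate in the excess time T2. The pooled rate (r1·T1 + r2·T2) / (T1 + T2) is below r1 only if r2 < r1. The documents give neither rate.

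**The case against.** The strongest objection is that the case may not arise. Protocol 4.1 and SAP 3.1 define completing Part A as finishing 52 weeks of double-blind treatment, and Protocol 4.2.2 opens Part B to those who complete Part A. Read strictly, an early stopper does not qualify. Other text assumes dosing up to about Week 52: Protocol 4.2.2 has subjects in remission stop blinded drug on entering Part B. This stands as a real uncertainty, but it does not settle the matter. SAP 9.1 defines completers by attendance, the Part B sets do not require completed treatment, and Protocol 5.4.1 and 5.4.2 keep early stoppers in the study.

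Second, the Week 52 cut has a purpose. SAP 11.5 starts Part B AEs at that visit or at the first open-label dose, so closing Part A there avoids double counting. That is right for anyone dosed to Week 36 or later, and the cut should stay. It does not explain why the last dose is ignored for earlier stoppers.

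Third, SC IP is not the only study treatment. SAP 5.1 tabulates subjects who stopped SC IP but completed prednisone study drug, so part of the excess time may be on prednisone. Even so, SAP 9.1 defines the window by SC IP, and the prednisone point applies equally to non-entrants, who are cut at 16 weeks.

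Fourth, the listings limit the harm. All AEs are listed and flagged (SAP 9.1.1), last-dose dates are listed (SAP 5.1), and the rates are descriptive. A reader could rebuild the consistent window subject by subject, but the summary tables would still carry the mixed rule.

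A reader might also infer that all off-drug time is miscounted. It is not: every class counts up to 16 weeks after the last dose, and only time beyond that is in question.

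**Conclusion.** The inconsistency is in the SAP text. For a Part B entrant whose last Part A SC IP dose was before about Week 36, SAP 9.1 counts events and person-time more than 16 weeks after that dose as treatment-emergent and exposed. SAP 7.2.1 and 11.5 use a 16-week window, as do the other two classes in 9.1 itself.

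The size is 36 − L weeks per event-free subject. At arm level this is about 1-7% of person-time if 5-10% of an arm is affected, with last doses between Weeks 4 and 24. Those shares are assumptions. SAP 1.1 cites the limited number of subjects who completed Week 52, so the true figure may be small or zero. It also depends on early stoppers having been admitted to Part B.

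Two stronger readings are tempting. One takes the per-subject ratio, such as 52 against 24 weeks (+117%) for a last dose at Week 8, as the size of the error. It describes one hypothetical person, not a reported rate. The other is that sirukumab rates are diluted. Extra person-time lowers a rate and late events raise it; the net effect depends on the late off-drug event rate, which is not given. The rule also applies to the placebo arms, so no bias between arms is shown.

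**What to change.** In SAP 9.1, replace the end point for Part B entrants with the earlier of (a) the Week 52 visit, or the first open-label dose if that comes first, and (b) last Part A SC IP dose + 16 weeks. This keeps the Part A/Part B cut, leaves subjects dosed to Week 36 or later unchanged apart from any first open-label dose before the Week 52 visit, and brings 9.1 and 9.1.1 into line with the 16-week window in 7.2.1 and 11.5.

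It would help to report how many Part B entrants had a last Part A SC IP dose before Week 36. The listed dates already supply this, and a count of zero would close the point.

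The cost is one line of text and slightly less counted exposure. No event is lost: AEs after the shortened window and before Part B move to the post-study-treatment summary that SAP 9.1.1 already plans. If no early stopper entered Part B, this part of the change alters no result.
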